5.6 Data Analysis

Aim 1

To address aim 1, we will conduct qualitative semi-structured (audio-recorded) interviews with both patient (N = 30, 15 per site) and provider (N=10, 5 per site) participants to help inform both the initial implementation and the re-versioning of the web-based BAI for two VA HCV clinics. Interviewing both patients and providers will allow us to better understand the patient, provider, and system factors that serve as potential facilitators or barriers to the adoption of a web-based BAI. Sampling from both clinics will provide information on similarities and differences across both sites in HCV care and adoption of a web-based BAI.

All interviews will be audio recorded by the study coordinator. The recordings may then be sent via a secure, encrypted online server to a medical transcription company for transcribing. The transcription process will occur as soon after each interview as possible. Audio data and de-identified transcript data will be maintained on the secure server at VAPAHCS in a folder accessible only to those study staff who are involved in data processing and analysis.

Supervision and quality review of the de-identified interview notes will be provided by [name] and Co-Is [Drs. [name] and [name]]. Template analysis (also known as thematic coding) will be used to identify themes in the textual data (King, 1998). The study coordinator and Co-I [name] will engage in the initial analysis of de-identified interview data. Following recommendations by King, the analysis process will initially be structured by the areas of content assessed in the patient and provider interviews. The study coordinator and [name] will consult regularly throughout data collection to discuss insights and unexpected responses from participants which may alter how some topics are addressed or how the interviews are structured.

After the interviews and transcriptions are complete, the study coordinator and [name] will begin developing two separate codebooks for patient and providers. Codebook development will be an iterative process. Codebooks will be initially developed based on close readings of 30% of patient (n = 9) and 40% (n = 4) of provider transcripts. Themes that emerge from the patient and provider interviews will be continuously integrated into their respective codebooks. We anticipate that the final set of themes will consist of both themes defined a priori and new themes that emerge from each set of interviews. Upon completion of the initial version of the codebooks, the study coordinator and [name] will discuss the application of the codebooks to each set of interviews. This process will involve practicing applying the codebooks to a single patient and provider interview. When agreement is reached, the study coordinator and [name] will code a random sample of 20% of patient (n = 6) and 20% of provider (n =2) interviews to establish inter rater reliability. Once reliability is established (80% agreement), we will proceed to code the remaining portion of the patient and provider transcripts. Throughout the coding process, the PI and [name] will regularly discuss emerging themes, changing conceptualizations of existing themes, and to prevent drift. They will also consult intermittently with the other Co-Is and consultants to discuss emerging themes and conceptualizations. After data coding is complete, data analysis will begin, focusing on the frequency of code occurrence (by participant and code) and patterns of code co-occurrence for each set of interviews.

Aim 2

Based on findings from prior studies of web-based BAIs with similar follow-up time

frames, we expect an average effect size of .35 to .40 (range is .15 to .67) on alcohol consumption outcomes in response to the web-based BAI (Kypri et al., 2004; Kypri et al., 2008; Neighbors et al., 2004). Assuming a power of 80% of detecting an effect size of .35, an alpha level of .05, a 2-tailed test, a correlation of .5 between repeated measures of an outcome variable, and a 20% attrition rate at 6 months, we estimate that we will need 170 individuals per condition at baseline for a total sample of 340 across both sites, with one half in the experimental condition and TAU condition at each site (i.e., n=85 per condition at Palo Alto, n=85 per condition at San Francisco).

Data Analysis

Prior to any regression modeling, we will first examine the sample distributions of each outcome variable and predictor variable to help us identify any possible errors in the data (e.g. coding errors). One of the benefits of our proposed use of generalized linear mixed model (GLMM) regression analyses is that it can accommodate a variety of conditional distributions for each outcome variable. Given that we will randomly assign participants to each condition, we expect the two groups to be comparable on baseline demographics and outcome variables at baseline. Nevertheless, we will conduct independent groups t-tests or chi-square analyses to check for any differences between the two groups on demographic characteristics and baseline outcome assessments. If differences are found between groups on any variables, we will control for those variables in subsequent analyses. Next, we will use generalized linear mixed-model (GLMM) regression analyses to compare the two conditions on our primary and secondary outcomes (Raudenbush et al., 2001; Singer et al., 2003). The primary hypothesis is that the slope of drinking outcomes over 0 to 6 months for participants in the web-based BAI plus TAU condition will differ from the TAU only condition. We will use the repeated measures data to fit a model consisting of fixed-effect terms for time since randomization, the time by condition interaction, and the site main effect. Random intercepts will be included to account for possible correlation among repeated measurements due to patient-specific latent factors. We will examine further constraints on the covariance structure and choose the final model by assessing goodness-of-fit. We will also examine the distribution of the outcome variables and associated random error components, choose appropriate link and variance functions (McCullagh & Nelder, 1991), and review any outliers.

Examining Mediators and Moderators

Prior studies show that the effectiveness of web-based BAIs is at least partly due to the correction of misperceptions about normative alcohol use (i.e., social norms; Borsari & Carey, 2001; Neighbors et al., 2004). Therefore, we will test whether changes in social norms (e.g., descriptive and injunctive norms) mediate the effect of the web-based BAI on alcohol consumption. Following the recommendation of Baron and Kenny (1986), we will conduct a series of analytic steps (using regression models) to determine mediation: (a) we will test the effect of both intervention conditions on alcohol consumption; (b) the effect of intervention conditions on social norms; (c) the effect of social norms on alcohol consumption controlling for intervention condition; and (d) the effect of intervention condition on alcohol consumption after controlling for social norms. In addition, we will examine potential moderators (e.g., severity of alcohol use, coping, psychological distress) that may impact the effectiveness of intervention condition on treatment outcome. This analysis will help us determine whether the effectiveness of the intervention(s) is impacted by these variables at baseline and over the course of each follow-up.

Missing Data Prevention, Detection, and Adjustment

We will make every effort to prevent missing data at each assessment by achieving as high a response rate as possible. Baseline data will be collected during an in-person interview and follow-up assessments will be conducted as telephone interviews by study site

coordinators who have been trained to cover all questions and obtain as complete data as possible while respecting the patient's right to not answer specific questions. Based on previous follow-up studies of SUD patients conducted at our Center, we do not expect rates of missing data on any one variable to be greater than 5% at each assessment over and above missing data due to attrition, nor do we expect missing data to be systematically related to certain outcome variables. Nevertheless, given our plan to use an intent-to-treat approach that includes all patients who are randomized in our GLMM regression models, we will use multiple imputation. Multiple imputation procedure yields more efficient, accurate, and reliable inferences than ad-hoc methods of handling missing data (such as list wise deletion or mean substitution) (Shafer, 1997 Shafer et al., 2002; Little & Rubin, 2002).

Formative Evaluation Data Analysis

The Co-PI ([name]) and study coordinator will compile de-identified notes collected from observations made from both site visits to generate written summaries of clinic characteristics and pictorial descriptions of clinic processes. We will pursue a rapid analysis (e.g., Sobo et al., 2005) of interview data (collected from site visit 2) to ensure quick translation of provider feedback to actionable revisions to the initial implementation plan. The study coordinator will listen to all interview tapes within two weeks of returning from the second site visit. The Co-PI ([name]) and study coordinator will compile all de-identified interview and observation notes, and create barrier and facilitator tables which will be commented on and revised by the PI and [name], site directors, and our Co-Is ([name], [name], [name]), who are experts in qualitative analysis and implementation science. From these data we will develop barrier/facilitator summary tables to inform revisions to the initial implementation plan. These data will inform actionable next steps which include providing further education to site staff and drafting locally-customized implementation strategies (e.g., placement of the intervention within clinic, suggestions for modifying point in care in which it is utilized) (Curran et al., 2008). Upon completion of the summary tables, the study team will conduct a more comprehensive analysis of the interview tapes. Analysis of Interview data will facilitate manuscript preparation.

Aim 3

As described above, we will estimate the average cost of the intervention. For each participant, we will summarize their utilization and cost data. We will then perform a budget impact analysis of the intervention, comparing all health care costs for each arm of the study, including the costs of the intervention (e.g. providing the web-based BAI). Consistent with guidelines (Mauskopf et al., 2007), we will not include costs of developing the intervention or administrative overhead. Assuming also, that the BAI may impact both immediate decisions about alcohol use as well as decisions about other health care in the near future, we will analyze all health care utilization and costs incurred within the 12 months following randomization. We will also compare costs incurred in the first 6 months to those incurred in the second six months. We will estimate the budgetary impact for the two sites involved with the study. We will then extrapolate from these sites to create projections for other VAMCs based on the prevalence of patients with HCV and alcohol use at each site. This will allow us to estimate the budget impact of diffusing the web-based BAI throughout the VA system. Economics data will be managed in the same way as the clinical data and housed at HERC. We will adopt the same procedures and policies developed in the Aim 2.

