Our second aim is to implement a re-versioned web-based BAI in two liver clinics and to evaluate the implementability and effectiveness of this intervention to reduce alcohol consumption in Veterans with liver disorders at three- and six-months post treatment. To achieve Aim 2, we will conduct a randomized controlled trial utilizing a hybrid (Type 1) design with patient-level clinical outcome data and formative evaluation data collected (Curran et al., 2008). Participants will be randomized to one of two treatment conditions –(a) web-based BAI plus treatment-as-usual (TAU) or (b) TAU only. We will also conduct a formative evaluation to determine the feasibility and challenges of implementing the web-based BAI into liver clinics.

Method for Randomization

We plan to use a stratified permuted block design for randomizing participants where participants are stratified by site (Palo Alto or San Francisco) and baseline severity of alcohol use (alcohol dependent, not alcohol dependent). Four randomization strata will be used: not alcohol dependent (Palo Alto), alcohol dependent (Palo Alto), not alcohol dependent (San Francisco), and alcohol dependent (San Francisco). Within each stratum, we will construct blocks of consecutive patients that vary randomly in size (either 8 or 12 participants). Each block will contain equal quantities of assignments to the two study arms arranged (permuted) in random order. A random mixture of block sizes of 8 and 12 will be used to prevent forecasting

of treatment assignments by project personnel since neither the participants nor the project staff will not be blinded to the assigned treatment condition.

Web-Based BAI Content

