(c) Patient satisfaction. We will use a brief patient survey that we developed from our preliminary work to assess patients' satisfaction with both treatment conditions. This survey will ask patients to respond to a series of statements regarding their satisfaction with the interventions received (e.g., "I felt comfortable disclosing my alcohol use to a computer program"; "My provider helped me understand how alcohol use may worsen liver disorder(s)."). This assessment will be completed by patients upon completion of the baseline assessment (and upon completion of the web-based BAI for patients assigned to the experimental condition).

Primary Outcomes.

(d) Alcohol quantity and frequency. Reduction in alcohol use will be measured using the 30-day Time Line Follow-Back instrument (TLFB; Sobell & Sobell, 1992). The TLFB is a calendar that provides visual cues to aid persons in retrospective recall of drinking behavior. It uses "cues" (e.g., holidays, birthdays) to help a participant recall drinking behavior (e.g., frequency and quantity of alcohol use) and has been shown to be reliable and accurate when administered individually over the telephone (Sobell et al., 1996). Based on recommendations from the alcohol treatment literature we will assess the *(a) number of drinking days, (b) mean number of drinks per drinking day, and (c) percentage of heavy drinking days* in the prior 30 days as our primary outcomes (Dieperink et al., 2010; Gastfriend et al., 2007). These outcomes will be measured by comparing TLFB drinking data at baseline (30-days prior) to data collected at three- and six-month follow-up (30 days prior).

Secondary Outcomes.

(e) Consequences of alcohol use. The Short Index of Problems (SIP-3months) is a brief, 15-item version of the Drinker Inventory of Consequences (DrInC) which assesses alcohol-related problems over the prior 3-months (Woolard et al., 2004). The SIP has sound psychometric properties (Kenna et al., 2005).

(f) Symptoms of psychological distress. Symptoms of psychological distress will be measured using the Brief Symptoms Inventory (BSI). The BSI instrument provides an overview of a patient's symptoms and their intensity at a specific point in time (Derogatis & Melisaratos, 1983). The reliability, validity, and clinical utility of the BSI instrument are well-established.

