(g) Health status. The Short Form-12 (SF-12) is a 12-item health survey based on the Medical Outcomes Study 36-item Short-Form Health Survey (SF-36) designed to assess two component health status summary scales (physical and mental component summaries) in the general U.S. population (Ware et al., 1996). The SF-12 has demonstrated good internal consistency reliability and construct validity (Luo et al., 2003).

(h) Seeking/receiving additional care. We will measure the degree to which Veteran participants seek additional SUD care over the course of the three- and six- month follow up periods. We will assess whether Veterans seek out outpatient/inpatient care of a substance abuse problem within or outside the VA system. We will also assess whether Veterans access self-help care outside the VA such as attending a meeting at Alcoholics Anonymous.

(i) Depressive symptoms. The Patient Health Questionnaire-9 (PHQ-9) is a 9-item depression scale based on the Diagnostic and Statistical Manual Fourth Edition (American Psychiatric Association, 2000). Items are scored (and summed) from 0 (not at all) to 3

(nearly every day), with severity of symptoms ranging from 0 to 27. The reliability and validity of the PHQ-9 are well established (Kroenke et al., 2001).

(j) Coping. The Coping Responses Inventory (CRI; Moos, 1993) will be used to assess participants' use of approach and avoidance coping strategies to manage stressful events (e.g., antiviral therapy). The CRI asks participants to identify their most significant stressor over the past 12 months, and then complete 48 items that describe specific coping strategies used to manage the stressor. Coping items are rated from 0 (not at all) to 3 (fairly often). The CRI comprises 8 subscales (e.g., problem solving) that have strong internal consistencies (Moos, 1993, 2002).

(k) Knowledge of HCV. This is a 16-item assessment of HCV knowledge based on patient education developed by the VA Hepatitis C Resource Center (2011). Total knowledge will be derived from percent of the questions answered correctly (ranging from 0 – 100%). Accuracy of HCV knowledge will be defined as percentage of correct answers with higher percentages reflecting more accurate HCV knowledge.

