(l) Social norms. Two questions will assess perceived quantity and frequency of alcohol consumption among participants' peers (i.e., descriptive norms, e.g., "How many drinks on one occasion do men/women your age consume?" [frequency]), while a 10-item measure will be used to assess concerns about harmful alcohol use (injunctive norms; Williams et al., 2009).

(m) Mini International Neuropsychiatric Interview (MINI). Section J, Alcohol Abuse and Dependence will measure the level of alcohol consumption over the past 30 days among participants. This is a 12-item assessment, with items rated from 0 (not at all) to 4 (extremely). This questionnaire will assess the presence of an alcohol use disorder (AUD) among participants.

Formative Evaluation Plan

We will utilize a well-established formative evaluation protocol that will include two site visits (to each study site) and interviews with staff (at each site) at three-month post initial implementation (e.g., Curran et al., 2008).

At the first site visit study staff will spend a day in each clinic reading program policy manuals and meeting with clinic directors. The latter will provide an opportunity to pose more focused questions on clinic policies (especially related to screening and treating current alcohol use). The meetings will be used to gauge clinic directors' support for the project as initial implementation will occur approximately one-year after funding notification. Therefore, it will be important to reassess clinic directors' current attitudes and beliefs, and answer any questions on the implementation process. When necessary we will provide brief, evidence summaries on the effectiveness of web-based BAIs and advocate VA practice guidelines for screening and treating alcohol use or misuse when appropriate.

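### Covariates other than site are chosen by baseline tests, and alcohol dependence, one of the two randomisation factors, is not in the listed primary model

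*Combined protocol and SAP*

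**What the plan says.** All of this concerns Aim 2.

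- **Baseline screen (5.6, Data Analysis).** The plan expects comparable arms but will still run "independent groups t-tests or chi-square analyses to check for any differences between the two groups on demographic characteristics and baseline outcome assessments". Next comes the rule: "If differences are found between groups on any variables, we will control for those variables in subsequent analyses". It gives no test level and no closed list of variables.
- **Primary model (same paragraph).** The hypothesis concerns the difference in slope over 0 to 6 months. The model has "fixed-effect terms for time since randomization, the time by condition interaction, and the site main effect", plus random intercepts. No condition main effect is listed.
- **Randomisation (5.1, Method for Randomization).** Permuted blocks of 8 or 12 are used, and "participants are stratified by site (Palo Alto or San Francisco) and baseline severity of alcohol use (alcohol dependent, not alcohol dependent").
- **Severity of alcohol use elsewhere in the Aim 2 analysis.** It returns only as a possible moderator.
- **Drinking outcomes (5.5, Primary Outcomes).** They are assessed by "comparing TLFB drinking data at baseline (30-days prior) to data collected at three- and six-month follow-up (30 days prior"), so the baseline value is also the time-0 response in the slope model.

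**The concern.** A baseline test in a randomised trial asks whether chance produced a difference, and the answer is already known. It says nothing about whether a variable predicts drinking, which is the reason to adjust. Under this rule the primary model depends on the allocation that happened to occur, on an unstated cut-off and on an unstated list of variables. Two analysts could follow the text and fit different models.

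Alcohol dependence has the opposite problem. It was judged important enough to stratify on, and stratification keeps it balanced, so a rule that admits only imbalanced variables will leave it out. At stake are a pre-specified primary analysis and a little precision. A false-positive result is not the main risk.

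**Working it through.** **1. The plan's own figure.** For an effect of .35, two-sided .05 and 80% power, n = 2(1.960 + 0.8416)²/0.35² = 128.1, so 129 per arm. Dividing by 0.80 for attrition gives 162, against 170 stated. The gap is on the safe side: allowing also for the 5% item missingness mentioned under missing data gives 129/(0.80 × 0.95) = 169.7. It does not affect this point. Below I use 170 × 0.80 = 136 completers per arm.

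**2. How many variables are screened.** From 5.5: age, gender, three drinking measures, SIP, BSI, two SF-12 scores, PHQ-9, two coping scores, HCV knowledge and three norms measures make 16. Using the eight coping subscales instead of two scores (+6), and adding SUD-treatment, mental-health and self-help history (+3), makes 25. The MINI is left out because stratification balances dependence.

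**3. Chance that the rule adds something.** With K independent tests at an assumed .05, P = 1 − 0.95^K. With equal pairwise correlation ρ, P is found by numerical integration over a shared normal factor.

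| K | ρ = 0 | ρ = .3 | ρ = .5 |
|---|---|---|---|
| 16 | 56% | 48% | 37% |
| 25 | 72% | 61% | 47% |

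**4. Chance that the rule adds dependence.** Stratified blocks of 8 and 12 were simulated at 20%, 35% and 50% dependent. Dependence was flagged in 0 of 12,000 trials (largest z 1.09). A separate set at 30% and 50% gave 0 of 288,000.

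**5. Cost of leaving the stratum out of the listed model.** Inputs: 136 per arm, times 0, 3 and 6 months scaled to 0, 0.5 and 1, total variance 1, correlation .5 (random-intercept and residual variance 0.5 each), effect .35 at 6 months. If a share p is dependent and the strata differ by d within-stratum SD, dependence explains R² = p(1 − p)d²/(1 + p(1 − p)d²). This runs from 0.0525/1.0525 = .05 (p = .3, d = 0.5) to 0.5625/1.5625 = .36 (p = .5, d = 1.5). The generalised least squares model SE without the stratum is 0.1034. The true SE is smaller because the strata are balanced. Then:

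- type I error, omitted = 2[1 − Φ(1.96 × 0.1034/SE_true)]
- power, omitted = Φ((0.35 − 1.96 × 0.1034)/SE_true)
- power, included = Φ(0.35/SE_incl − 1.96)

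| R² | SE_true | SE_incl | Type I, omitted | Power, omitted | Power, included |
|---|---|---|---|---|---|
| .05 | .1024 | .1023 | 4.8% | 92.5% | 92.8% |
| .10 | .1013 | .1010 | 4.5% | 92.7% | 93.4% |
| .20 | .0991 | .0979 | 4.1% | 93.1% | 94.7% |
| .30 | .0969 | .0935 | 3.6% | 93.6% | 96.3% |
| .36 | .0955 | .0900 | 3.4% | 93.9% | 97.3% |

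Simulation of the same model over the same ranges (12,000 trials per setting) gave gains of 0.4 to 3.6 points and type I error of 3.5% to 5.2% with the stratum omitted. With 10% missing at 3 months and 20% at 6 months, power was 93.2% omitted against 93.5% included at 0.5 SD, and 90.5% against 92.6% at 1.5 SD.

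If a condition main effect is added, the slope test uses only within-person change. Its SE is √(2 × (0.5/0.5)/136) = 0.1213, and power is Φ(0.35/0.1213 − 1.96) = 82.3% with or without the stratum (complete data).

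**6. An outcome's own baseline.** Nothing in the rule's wording excludes it. If it were added it would serve both as time-0 response and as covariate. Its chance of being flagged at .05 is 5% if dependence is not prognostic. If it is, exact balance gives 2[1 − Φ(1.96/√(1 − R²))], which is 4.4% at R² = .05 and 1.4% at R² = .36. Simulation with the actual blocks gave 1.6% to 4.7% for one drinking measure, and about 4% to 11% for at least one of the three.

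**The case against.** The strongest reply is that little is at risk. The listed model keeps about 89% to 94% power without the stratum, above the planned 80%. The random intercept absorbs stable differences such as dependence, so the test is conservative rather than invalid. Site is already pre-specified, and the listed model already uses each baseline once. All of this stands, and it limits the point to pre-specification and modest precision.

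It is also fair that the fix does not close the model completely. Section 5.6 still chooses covariance structure, link and variance functions after looking at the data.

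A reader might infer that the rule inflates type I error to about 20%. Simulation does give 19% to 21%, but only in trials where an outcome's own baseline is flagged and then added as a covariate. The plan does not say it would be added. Such trials are at most about 5% per outcome, and an ordinary slope model with a condition main effect shows 16.5% to 18.7% in the same trials. Over all trials, even on that reading and with dependence taken as not prognostic, the figure is 5.9% to 6.1%, against 5.2% to 5.4% without the rule. This is a caution about wording only.

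A reader might also argue that dependence could enter through the screen because the MINI is among the baseline measures ("This questionnaire will assess the presence of an alcohol use disorder (AUD) among participants"). Step 4 shows why that route is closed in practice.

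**Conclusion.** The point holds as a matter of pre-specification, with modest harm. Baseline tests select every covariate except site, and the rule would probably add something in many trials (roughly 37% to 72%, given an assumed .05 level and 16 to 25 variables). One of the two randomisation factors is missing from the listed model, and the rule cannot supply it. Omission costs about 0 to 3.6 power points and leaves type I error at about 3.5% to 5%. The possible double use of an outcome's own baseline is secondary and rests on one reading of the rule.

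The documents do not support reading this as an underpowered trial or as one with a materially inflated error rate. The power figures depend on the assumed prevalence and prognostic strength of dependence and on approximately normal outcomes. Multiple imputation and the percentage outcome were not modelled, so the decimals should not be pressed.

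**What to change.** In 5.6, delete "If differences are found between groups on any variables, we will control for those variables in subsequent analyses" and keep the baseline comparison as description only. Insert:

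> Covariates are fixed in advance and do not depend on baseline tests. The models for the primary drinking outcomes, and for secondary outcomes measured at baseline, include site and alcohol-dependence stratum as fixed effects. Each outcome's baseline value is used once only, as the time-0 response.

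The cost is one degree of freedom for the stratum. No new data, visits or participants are needed, since dependence must already be known in order to randomise.

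### The primary slope model names no 3-month contrast and, with time linear, fixes the 3-month arm difference at half the 6-month one, although the trial asks about both visits

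*Combined protocol and SAP*

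**What the plan says.** Section 5.6 (Data Analysis, Aim 2) gives one primary hypothesis for the drinking outcomes: "the slope of drinking outcomes over 0 to 6 months for participants in the web-based BAI plus TAU condition will differ" from that in the TAU-only arm. The analysts will "fit a model consisting of fixed-effect terms for time since randomization, the time by condition interaction, and the site main effect". On the correlation structure it says "Random intercepts will be included to account for possible correlation among repeated measurements", followed by "We will examine further constraints on the covariance structure and choose the final model by assessing goodness-of-fit". The link function is left open. There is no condition main effect, visit indicator, curved or piecewise time term, or visit-specific contrast.

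Other sections put the question at two visits. Section 5.1 (Aim 2) sets out to evaluate whether the intervention works "to reduce alcohol consumption in Veterans with liver disorders at three- and six-months post treatment", and section 3.0 repeats this. Section 5.5 measures the primary outcomes by "comparing TLFB drinking data at baseline (30-days prior) to data collected at three- and six-month follow-up (30 days prior"). The hypotheses in section 3.0 also mention both times, but the phrase closes H3 and need not govern H1, so Aim 2 and section 5.5 are the firmer support.

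For sample size, section 5.6 says "we expect an average effect size of .35 to .40 (range is .15 to .67) on alcohol consumption outcomes" and plans on .35, without tying that figure to a visit.

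**The concern.** With linear time and time by condition as the only treatment term, the arm difference at month t is b × t. The ratio of the 3-month to the 6-month difference is therefore 3b/6b = .5 by construction. A 3-month effect read from this model is wrong unless the true effect exactly doubles between the visits, and the plan names no other 3-month estimate.

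The intervention is given once, at baseline (section 4.0), and section 2.0 cites a trial in college students that reported reductions by six weeks. An effect already present at month 3 that does not double by month 6 is a reasonable case to plan for. The documents give no time course for this population, so that is a possibility and not a prediction.

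Two things are at stake: a missing or misstated 3-month answer to Aim 2, and, if the effect fades, a primary test weaker than one that uses both visits evenly.

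**Working it through.** **The plan's own figure.** For effect .35, two-sided alpha .05 and 80% power, n = 2(1.960 + 0.842)²/.35², which rounds up to 129 per arm. With correlation .5 the change-score factor 2(1 − .5) = 1 leaves it at 129. Dividing by .80 gives 162. The stated 170 is reached only by also allowing the 5% item-level missingness mentioned later in section 5.6: 129/(.80 × .95) = 169.7. The plan does not make that link, and it does not affect this point.

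**Inputs.** From section 5.6: correlation .5, 170 per arm, 20% attrition at 6 months, random intercepts (compound symmetry). Hence 170 × .80 = 136 per arm, used here at every visit. SD is 1. True differences are 0, d3 and d6 at months 0, 3 and 6; baseline means are equal by randomization. The d3/d6 pairs are assumptions.

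**What the linear model estimates.** The inverse correlation matrix has 1.5 on the diagonal and −.5 elsewhere. With time scored 0, 1, 2, generalized least squares gives

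- fitted 6-month difference = (0.5·d3 + 2.5·d6)/2.75 = .182·d3 + .909·d6
- fitted 3-month difference = half of that = .091·d3 + .455·d6, which equals d3 only if d6 = 2·d3.

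For .35/.35: 6-month fit = .064 + .318 = .382; 3-month fit = .191. With correlation .3 to .7 the 3-month fit is .20 to .18.

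**Standard errors.**

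- Slope, on the 6-month scale: √[(4/5.5)(2/136)] = .103
- Each visit, time categorical: √(.75 × 2/136) = .105
- Average of the two visits: √(.5 × 2/136) = .0857
- Joint 2-df test: noncentrality 68(1.5·d3² + 1.5·d6² − d3·d6)

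Example, .35/.20: slope .2455/.1034 = 2.37, power Φ(2.37 − 1.96) = 66%; average .275/.0857 = 3.21, power 89%.

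| True d3/d6 | Fitted at month 3 | Slope | Average | Joint 2-df | Month 6 alone |
|---|---|---|---|---|---|
| .35/.35 | .19 | 96% | 98% | 96% | 92% |
| .35/.25 | .15 | 80% | 94% | 91% | 66% |
| .35/.20 | .12 | 66% | 89% | 88% | 48% |
| .35/.15 | .10 | 49% | 83% | 86% | 30% |
| .35/0 | .03 | 9% | 53% | 90% | 5% |
| .50/.35 | .20 | 98% | >99% | >99% | 92% |
| .175/.35 | .175 | 92% | 86% | 87% | 92% |

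Wherever d3 = .35, a 3-month contrast from the categorical model has about 92% power (.35/.105 = 3.33).

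**Sensitivity.** With 170/153/136 observed per arm (10% loss at month 3 is an assumption), slope against average is 97% v 99% for .35/.35, 85% v 95% for .35/.25, 72% v 92% for .35/.20 and 56% v 86% for .35/.15. With correlation .3 or .7, .35/.20 gives 66% v 86% or 75% v 97%.

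**Log link.** The 3-month log ratio is half the 6-month log ratio. If the true rate ratio is .75 at both visits, the normal-theory weights give (.182 + .909)/2 = .545 and exp(.545 × ln .75) = .855 at month 3. Random-intercept Poisson simulations in four assumed settings gave .847 to .868; the categorical model gave .75 to .76.

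**The case against.** The constraint depends on how time is coded, and section 5.6 never says linear. If visit were categorical, the interaction would already contain 3- and 6-month terms, and only the naming of contrasts would be missing. That is right, but the word slope and a single time term favour the linear reading. Under the other reading the plan still names neither a 3-month contrast nor a primary one.

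The plan also does not say that a 3-month effect will be read from the slope. So the certain defect is that the estimate is missing; it is misstated only if someone derives it from the fitted line.

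A slope is a legitimate single estimand. It is the most powerful of the three multi-visit tests under linear growth, and it matches or beats a 6-month contrast in every row of the table. It reaches the planned 80% for sustained, linear and mildly fading effects. All of this stands, and the power argument is therefore secondary and applies to assumed fades.

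The goodness-of-fit sentence might be read to cover the time trend. Its more natural reading is the covariance structure only, and the broader reading would let the data choose the primary estimand.

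Finally, the powers are on a normal scale, while the outcomes are day counts, drinks per drinking day and a percentage. They do not transfer directly; the half constraint on the link scale does.

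**Conclusion.** The concern holds. As written, the primary analysis gives no specified 3-month arm difference. With linear time and no condition main effect, the one it implies is half the 6-month value regardless of the data. For a sustained effect of .35 the implied 3-month value is .19, slightly more than half the truth, with almost no loss of power for the test itself.

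A material power loss arises only if the effect fades: 66% against 89% for .35/.20, and 49% against 83% for .35/.15. These figures rest on normal theory, correlation .5, 136 per arm and assumed time courses. The half constraint rests only on linear time and the listed fixed effects. Confidence is high on the missing contrast; the constraint carries the stated condition about how time is coded. The change should be made, though the trial's data collection is unaffected.

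**What to change.** Fit visit (0, 3, 6 months) as a category with a common baseline mean and condition-by-visit terms at months 3 and 6. Report each visit's effect with its confidence interval. Name one primary contrast per outcome from this model: either the average of the two follow-up differences, which is strongest if the effect is sustained, or the joint 2-df test, which holds up better if the effect is mainly early. The slope can remain as a secondary summary. If it stays primary, state that time is linear and add the 3- and 6-month effects from the categorical model as named estimates.

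Three primary outcomes at two visits give six intervals. The SAP should say that these are estimates supporting the primary contrast and not six further tests. Multiplicity across the three outcomes needs its own rule.

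The cost is SAP wording and two extra fixed-effect parameters (four visit and condition-by-visit terms in place of two), with no new data or patients. If the effect truly grows linearly from zero, the average has about 6 points less power than the slope (92.3% − 86.5% = 5.8). If the effect is sustained, the joint test has about 2 points less than the average (96% v 98%).
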